
DLT PERIOD AND DEFINITION OF DLTS
	
The DLT period is defined as Cycle 1*.
 
DLT is defined as any of the following treatment-emergent adverse events (TEAEs) which are possibly, probably or definitely related to the combination treatment and occurring in Cycle 1 (1 cycle=4 weeks):
 
 
• Any Grade 4 or 5 hematologic toxicity, clinical or laboratory non-hematologic toxicity
 
• Febrile neutropenia any grade, Grade 3 thrombocytopenia if associated with bleeding or requiring platelet transfusion
 
• Grade 2 or higher cardiac or neurologic toxicities, pneumonitis that does not resolve within 3 days after starting steroids at adequate doses or that was recurrent upon steroid tapering or withdrawal, myasthenia gravis, myositis, polymyositis, Guillain-Barre syndrome (excluding peripheral purely-sensory neuropathies)
 
• Grade 2 or higher alanine transaminase (ALT)/ aspartate transaminase (AST) increase with a concurrent increase of total bilirubin <math>\geq 2</math> x upper limit of normal (ULN) and concurrent with alkaline phosphatase (ALP) <math>\leq 2</math> x ULN (Hy's law), in the absence of objective causes of biliary obstruction due to obvious disease-related causes
 
• Any other Grade 3 non-hematologic, treatment-related clinical toxicity lasting 3 or more days despite optimal supportive care, or requiring admission for appropriate medical management; hypersensitivity and/or infusion-related reactions are excluded if not reoccurring after appropriate pre-medication and/or prolonging infusion time
 
• Grade 3 non-hematologic laboratory value (excluding lipase, amylase and/or autoimmune endocrinopathies manageable by replacement therapies) if:             
 
a. Symptomatic and
 
b. Medical intervention was promptly required to treat the patient, or
 
c. The abnormality led to hospitalization or
 
d. The abnormality did not resolve to at least Grade 1 within 2 weeks (including the steroid tapering period) despite adequate medical intervention/treatment
 
 
 
• A delay of >2 weeks due to drug-related toxicity in initiating Cycle 2
 
• Unable to complete at least 70% of the scheduled treatment, i.e., more than six Debio 1143 skipped doses in Cycle 1 due to treatment-related toxicity
 
• Required dose reduction in Cycle 1 or on Cycle 2 Day 1 or requirement for treatment withdrawal due to treatment-related toxicity (even if not meeting other DLT criteria)
 
 
* Any toxicity fulfilling one or more of these criteria but occurring from C2D1, may be defined as delayed DLTs after discussion and agreement between Principal Investigators (PIs), DSMC and the Sponsor, and may be considered for RP2D definition, if appropriate.

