	
Debio 1143 will be administered on site on D1 and D15, immediately before nivolumab. Remaining daily doses are to be taken by the patient at home following relevant medical instructions, except on days where PK samples are planned, during the first cycle, and the third cycle. Administration compliance will be recorded in a patient diary which will be supplied as a separate document.
 
Nivolumab will be administered, as per current prescribing information, at a dose of 240 mg, flat dose by IV infusion over at least 30 minutes on Days 1 and 15, q4w (i.e., 2 infusions per cycle). From Cycle 3 on, patients may be switched to nivolumab infusion at a dose of 480 mg over at least 60 minutes on Day 1 exclusively q4w (i.e., 1 infusion per cycle), upon the Investigator's request and Sponsor approval. Neither lower nor higher doses of nivolumab will be explored; dose reduction or increase will not be allowed.
 
Infusion of nivolumab will be stopped in case of Grade <math>\geq 2</math> hypersensitivity, inflammatory response, or infusion-related reactions. Infusions may be resumed after Grade <math>\leq 2</math> events upon resolution of the events within less than 4 hours and after medical assessment and agreement by a qualified Investigator. Infusion duration will not be shorter than 120 minutes after resumption in all subsequent infusions. Treatment will be withdrawn definitively after the occurrence of any Grade <math>\geq 3</math> infusion-related reactions, hypersensitivity or cytokine-release syndrome. Appropriate standard measures must be in place for the medical management of the patients under these circumstances.
 
Formal premedication is not required. However, premedication might be used after C1D1 administration, if needed on an individual patient basis, per clinical judgment and local institutional guidelines, as appropriate.

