
TREATMENT DURATION
	
Participants are planned to be treated with Debio 1143 and nivolumab for up to 52 weeks (13 cycles), until any of the following events occurs: symptomatic PD, asymptomatic but confirmed PD (as per iRECIST), unacceptable toxicity per Investigator judgment and despite up to two dose adjustments, patient withdrawal, or treatment delay greater than 4 and 8 weeks (+1 week tolerance) for Debio 1143 and nivolumab, respectively.
 
Permission to prolong the study treatment for one additional year can be exceptionally granted by the Sponsor, if patients are deriving continuous clinical benefit from the study treatment. Medical justification for extending the treatment and the assessment of the risk/benefit balance must be provided by the Study Investigator and will be discussed with the Sponsor. The decision to further extend study treatment will be re-evaluated on a yearly basis for each patient.
 
Re-treatment criteria are listed in Table 2.
 
From Cycle 2, if a patient does not meet the requirements for treatment continuation on Day 1 of any cycle, both study drugs will be withheld until recovery or for a maximum of 4 and 8 weeks (+1 week tolerance window) for Debio 1143 and nivolumab, respectively. After this delay-period, the patient should withdraw from treatment.
 
If a patient does not meet the requirements for treatment continuation on any days other than D1 (D2-10 or D15-24), treatment will be immediately interrupted and the corresponding Debio 1143 dose (and nivolumab if on D15) will be omitted. Patients should be re-assessed (ideally every 48-72 hours, if clinically indicated) and treatment will only be resumed after all re-treatment criteria are met.
 
All patients who withdraw from treatment for any reason will be followed for safety up to 5 months (<math>\pm 15</math> days) after the last nivolumab infusion, complete resolution or stabilization of any ongoing toxicity, unless the patient starts a new treatment, end-of-life-care or withdraws consent.
 
If for any reason, treatment with nivolumab is temporarily withheld, Debio 1143 may be continued; however, at any time, and regardless of the reason, if nivolumab is permanently discontinued then Debio 1143 must also be withdrawn. If for any reason Debio 1143 is withheld temporarily, nivolumab will also be withheld until treatment may be resumed. Patients will not receive any further nivolumab infusions during the study until Debio 1143 treatment is resumed.

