## 5.2. DLT period and definition of DLTs

The DLT period is defined as Cycle 1\*.

DLT is defined as any of the following treatment-emergent adverse events (TEAEs) which are possibly, probably or definitely related to the combination treatment and occurring in Cycle 1 (1 cycle=4 weeks):

- Any Grade 4 or 5 hematologic toxicity, clinical or laboratory non-hematologic toxicity
- Febrile neutropenia any grade, Grade 3 thrombocytopenia if associated with bleeding or requiring platelet transfusion
- Grade 2 or higher cardiac or neurologic toxicities, pneumonitis that does not resolve within 3 days after starting steroids at adequate doses or that was recurrent upon steroid tapering or withdrawal, myasthenia gravis, myositis, polymyositis, Guillain-Barre syndrome (excluding peripheral purely-sensory neuropathies)
- Grade 2 or higher alanine transaminase (ALT)/ aspartate transaminase (AST) increase with a concurrent increase of total bilirubin  $\geq 2$  x upper limit of normal (ULN) and concurrent with alkaline phosphatase (ALP)  $\leq 2$  x ULN (Hy's law), in the absence of objective causes of biliary obstruction due to obvious disease-related causes
- Any other Grade 3 non-hematologic, treatment-related clinical toxicity lasting 3 or more days despite optimal supportive care, or requiring admission for appropriate medical management; hypersensitivity and/or infusion-related reactions are excluded if not reoccurring after appropriate pre-medication and/or prolonging infusion time
- Grade 3 non-hematologic laboratory value (excluding lipase, amylase and/or autoimmune endocrinopathies manageable by replacement therapies) if:
  - a. Symptomatic and
  - b. Medical intervention was promptly required to treat the patient, or
  - c. The abnormality led to hospitalization or
  - d. The abnormality did not resolve to at least Grade 1 within 2 weeks (including the steroid tapering period) despite adequate medical intervention/treatment
- A delay of >2 weeks due to drug-related toxicity in initiating Cycle 2
- Unable to complete at least 70% of the scheduled treatment, i.e. more than six Debio 1143 skipped doses in Cycle 1 due to treatment-related toxicity
- Required dose reduction in Cycle 1 or on Cycle 2 Day 1 or requirement for treatment withdrawal due to treatment-related toxicity (even if not meeting other DLT criteria)

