**Study treatments**

Patients will receive oral Debio 1143 at a starting dose of 150 mg once daily on Days 1-10 and Days 15-24 every 4 weeks (q4w) along with nivolumab at a flat dose of 240 mg IV on days 1 and 15 of a 28-day cycle (with a possible switch to one dose at 480 mg q4w from Cycle 3) (cf. Table 5-1). On Days 1 and 15, Debio 1143 will be administered on site, immediately before the nivolumab infusion. Remaining daily doses are to be taken by the patient at home following relevant medical instructions, except on days where PK samples are planned, during the first cycle, and the third cycle. For nivolumab administration, specific precautionary measures outlined in section 7.6.2 must be applied.

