**Table 7-1 Treatment modification for symptoms of infusion-related reactions associated with nivolumab**

NCI-CTCAE grade and description	Treatment modification for nivolumab
Grade 1 – mild Mild transient reaction; infusion interruption not indicated; intervention not indicated.	
 
The total infusion time for nivolumab should not exceed 120 minutes.
 

Grade 2 – moderate Therapy or infusion interruption indicated but responds promptly to symptomatic treatment (for example, antihistamines, nonsteroidal anti-inflammatory drugs, narcotics, IV fluids); prophylactic medications indicated for $\leq 24$ h	
 
Stop nivolumab infusion.
 
Resume infusion at 50% of previous rate once infusion-related reaction has resolved or decreased to at least Grade 1 and monitor closely for any worsening.
 

Grade 3 – severe Prolonged (for example, not rapidly responsive to symptomatic medication and/or brief interruption of infusion); recurrence of symptoms following initial improvement; hospitalization indicated for clinical sequelae.	
 
Stop the nivolumab infusion immediately and disconnect infusion tubing from the patient.
 
Patients have to be withdrawn immediately from nivolumab treatment and must not receive any further nivolumab treatment.
 

Grade 4 – life-threatening Life-threatening consequences; urgent intervention indicated.	

If a patient experiences a Grade 3 or Grade 4 infusion-related reaction at any time, the patient must discontinue nivolumab. If an infusion reaction occurs, all details about drug preparation and infusion must be recorded.

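### The ungraded 4-hour paragraph in 7.6.2.2 and the 5.4 dose-reduction list conflict with permanent withdrawal after a Grade 3 infusion reaction; the DLT count is not affected

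*Protocol*

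**What the plan says.** **Withdrawal rule.** The synopsis (investigational products) and Protocol 7.6.2.2 both state: "Treatment will be withdrawn definitively after the occurrence of any Grade" 3 or higher infusion-related reaction, hypersensitivity or cytokine-release syndrome. Below Table 7-1 the protocol adds: "If a patient experiences a Grade 3 or Grade 4 infusion-related reaction at any time, the patient must discontinue nivolumab". Debio 1143 follows, because "if nivolumab is permanently discontinued then Debio 1143 must also be withdrawn" (synopsis, treatment duration). Section 5.4 and item 2 of 8.3.2.1 say the same.

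**The 4-hour paragraph of 7.6.2.2.** If a reaction has not fully resolved after 4 hours of appropriate management, the current infusion is not resumed. With the investigator's agreement, later infusions are given more slowly (120 to 180 minutes), and premedication may be considered. No grade is named.

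**Section 5.4.** The dose-reduction list sits under an instruction to restart treatment at a reduced Debio 1143 dose. One bullet covers Grade 3 related clinical toxicity that lasts 3 days or more or needs admission, and it carries the non-recurrence exclusion. A later sentence has patients who interrupt or delay for Grade 3 related toxicity resume after dose adjustment. Its parenthesis lists toxicities exempt from the adjustment.

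**Section 5.2.** The matching DLT bullet, also in the synopsis, has the same exclusion, which covers hypersensitivity as well: "infusion-related reactions are excluded if not reoccurring after appropriate pre-medication and/or prolonging infusion time". Two other bullets in that list make a DLT of "more than six Debio 1143 skipped doses in Cycle 1 due to treatment-related toxicity" and of a "requirement for treatment withdrawal due to treatment-related toxicity (even if not meeting other DLT criteria").

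**The concern.** Whether a reaction recurs can be seen only by giving nivolumab again. An exclusion that turns on recurrence therefore sits awkwardly in Grade 3 bullets when a Grade 3 reaction ends nivolumab. The practical risk is re-exposure. A site dealing with a reaction still present at 4 hours can find a paragraph that plans the next infusion and a table row that forbids it. 7.6.2.2 also refers to 5.4, together with 7.6.2.3, for reactions that are not immune-related, and in 5.4 the site meets a restart list and a general resume sentence. Whether a patient is re-exposed after a severe reaction should not depend on which section is read last. This applies in both parts of the study.

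**Working it through.** The plan gives no figure to reproduce for the conflict itself, so steps 1 and 2 set the texts side by side. Steps 3 and 4 use arithmetic.

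**1. The 4-hour paragraph against Table 7-1.**
- Table 7-1, Grade 2: the reaction responds promptly to symptomatic treatment. The infusion may resume at half rate once the reaction has resolved or fallen to Grade 1.
- Table 7-1, Grade 3: the reaction is prolonged, for example not rapidly responsive to medication or to a brief interruption. No hour limit is given. No further nivolumab is allowed.
- 7.6.2.2: not fully resolved at 4 hours despite management. Later infusions are slower.

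A reaction that has not responded by 4 hours fits both the Grade 3 row and the 4-hour paragraph, and the two give opposite instructions. A reaction that falls promptly to Grade 1 but lingers past 4 hours fits only the paragraph. A grade limit therefore leaves the paragraph with a use.

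**2. The 5.4 list against the withdrawal rule.** Take a Grade 2 reaction on Day 1, a slower premedicated infusion on Day 15, and a Grade 3 reaction then that needs admission.
- The exclusion removes only reactions that do not recur, so this one stays on the list. The list calls for a restart at a reduced Debio 1143 dose.
- 7.6.2.2 and Table 7-1 stop nivolumab for good, and Debio 1143 stops with it. No restart is possible.
- The general Grade 3 resume sentence in 5.4 does not say that 7.6.2 takes precedence.

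**3. The clause in 5.2.** Cycle 1 has Debio 1143 doses on Days 1-10 and 15-24, so 10 + 10 = 20. The 70% bullet allows six skipped doses: 20 − 6 = 14, and 14/20 = 70%. On timing, 5.3 says: "On Days 1 and 15, Debio 1143 will be administered on site, immediately before the nivolumab infusion".
- Withdrawal at the Day 1 infusion: 1 taken, 20 − 1 = 19 skipped, 1/20 = 5%.
- Withdrawal at the Day 15 infusion: at most 10 + 1 = 11 taken, at least 9 skipped, 11/20 = 55%.

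Both exceed six skipped doses, so the 70% bullet is met. The withdrawal bullet is met as well. A related Grade 3 reaction in Cycle 1, managed per protocol, is a DLT whether or not bullet five excludes it. Under 11.5.1 and SAP 6.2 the patient is then evaluable whatever the exposure.

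**4. The 3+3 count.** The limit is fewer than one-third of evaluable patients with a DLT. 1/6 = 16.7% is below it and 2/6 = 33.3% is not, so one event can decide a dose. By step 3, however, the event is counted with or without the clause, so the text read as a whole does not move the count.

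**The case against.** The best defence is that the protocol puts a general rule in 5.4 and specific overrides in 7.6.2. Withdrawal after a Grade 3 reaction is stated in three places, and 5.4 itself says that permanent nivolumab discontinuation ends Debio 1143. Grade 3 pneumonitis and Grade 3 hepatic and renal immune-related events also require permanent discontinuation in Table 7-2, and 5.4 does not name them either. The 4-hour paragraph comes after the withdrawal sentence and reads as the counterpart of the rule allowing resumption when Grade 2 or lower events resolve in under 4 hours. It was probably meant for those grades. The cross-reference in 7.6.2.2 names 7.6.2.3, which holds Table 7-1, as well as 5.4. DLT answers in the eCRF are confirmed at dose decisions (SAP 18.1.2), and the DSMC reviews the data.

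Most of this stands: a careful reader reaches the right action. But the order of paragraphs does not supply a grade, and nothing in 5.4 says that 7.6.2 prevails. The controls over DLT coding also do not address re-exposure at the site.

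A reader might infer that the non-recurrence condition can never be tested in a patient treated per protocol. That goes too far. A Grade 2 reaction may be re-infused and may return as Grade 3, and the clause does not state the grade of the earlier reaction.

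**Conclusion.** The point holds as a wording conflict about re-exposure, located in the 4-hour paragraph of 7.6.2.2 and in the 5.4 list and resume sentence. It is worth correcting for patient safety. Its frequency cannot be stated, because the documents give no rate of infusion reactions for this combination. SAP 4.3 records that the Part B cohorts were futile, so remaining exposure may be limited.

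Two stronger readings are not supported. A reader might infer that the 5.2 clause lets a Grade 3 reaction go uncounted and so turns 2/6 into 1/6. The 5.2 bullets are alternatives, so an exclusion in one does not cancel the others, and the last bullet applies even when no other criterion is met. A reader might also infer that the exclusion permits re-infusion after a Grade 3 reaction. It only classifies events.

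The conclusion on the DLT count assumes that the reaction is judged treatment-related, occurs at a Cycle 1 infusion, and is followed by the required withdrawal.

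**What to change.** 1. In 7.6.2.2, limit the 4-hour paragraph to reactions that are Grade 2 or lower by Table 7-1. State that reactions meeting the Grade 3 description follow the withdrawal rule.
2. In the 5.4 list, replace the exclusion clause with: *Grade 3 or higher hypersensitivity and infusion-related reactions are not a dose-reduction trigger and lead to permanent withdrawal per 7.6.2.2 and Table 7-1.* Simple deletion would be wrong here, because it would bring non-recurring Grade 3 reactions onto the restart list too.
3. After the Grade 3 resume sentence in 5.4, add a separate sentence saying that it does not apply where 7.6.2 requires permanent discontinuation. Do not add infusion reactions to the parenthesis. That parenthesis exempts toxicities from dose adjustment, so the addition could be read as permission to resume at the same dose.
4. Optional: delete the non-recurrence clause from 5.2 and the synopsis, where it does not change the classification of a Grade 3 reaction managed per protocol.

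The cost is protocol wording only: a grade limit and one statement in 7.6.2.2, one clause replaced and one sentence added in 5.4, and, if wanted, one clause deleted in two places. Visits, data collection and the SAP are unchanged.

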## 5.3. Study treatments

### Debio 1143: rationale for dose regimen

Since Debio 1143 is a chemosensitizer, radiosensitizer and immunosensitizer, its schedule of administration in clinical trials is adapted to the standard treatment used in the combination.

A 10-day on / 4-days off schedule given every 2 weeks (i.e., repeated twice in a 4-week cycle) of Debio 1143 was selected to optimize the activity of the combination with standard nivolumab. This schedule is being tested in an ongoing Debio 1143-NSCLC-105 study in combination with avelumab (NCT03270176). The 4-day wash-out period allows recovery from potential Debio 1143-related toxicity and gives a lower

cumulative dose per cycle than regimens using 14 days q3w (14 days on and 7 days off) while providing similar dose-density and intensity. As of 31 July 2018 (IDB cut-off), up to 13 patients had been treated in the Debio 1143-NSCLC-105 study: all 4 planned dose levels (150 to 250 mg/d) had been explored without reaching a formal MTD. No unexpected toxicities were observed and the 200 mg/d dose is currently being expanded formally.

In the first-in-human phase I single-agent trial, Debio 1143 was well tolerated up to doses of 900 mg/d on Days 1-5 every 3 weeks (q3w) and up to 400 mg/d Days 1-14 q3w. The MTD was not reached for either of these schedules. The prolonged dosing schedule of Debio 1143 with a total cumulative dose of 5600 mg/cycle showed good tolerability, with an acceptable toxicity profile and treatment compliance, similar to the short-course regimen at the highest explored dose level (i.e., total cumulative dose of 4500 mg/cycle). PDy demonstration of target occupancy and linear PK were observed within the explored dose range, even at doses as low as 120 mg/d. High interpatient variability was seen, but without drug-accumulation. The dose of 200 mg/d was chosen as the RP2D when Debio 1143 was combined with both cisplatin-based chemo-radiation (100 mg/m^2 IV on Day 2 q3w) in patients with locally advanced SCCHN, and with carboplatin and paclitaxel q3w in patients with NSCLC, triple-negative breast cancer or ovarian cancer [cf. section 6.2.1.4.5 of Debio 1143 Investigator’s Brochure and (28)]. It is therefore expected that a Debio 1143 starting dose of 150 mg/d, given orally on Days 1-10 and Days 15-24 q4w, with a dose-intensity of 750 mg/week and a maximal cumulative dose of 3000 mg per cycle is tolerable, relevant in terms of biological target engagement and feasible as single agent and in combination with standard dose of nivolumab.

Given that a linear dose-effect response was not observed above 120 mg/d in the single agent mechanistic studies, and that no further PDy effects are expected when the Debio 1143 dose is increased, dose escalation beyond 200 mg/d is not planned in this study.

**Study treatments**

Patients will receive oral Debio 1143 at a starting dose of 150 mg once daily on Days 1-10 and Days 15-24 every 4 weeks (q4w) along with nivolumab at a flat dose of 240 mg IV on days 1 and 15 of a 28-day cycle (with a possible switch to one dose at 480 mg q4w from Cycle 3) (cf. Table 5-1). On Days 1 and 15, Debio 1143 will be administered on site, immediately before the nivolumab infusion. Remaining daily doses are to be taken by the patient at home following relevant medical instructions, except on days where PK samples are planned, during the first cycle, and the third cycle. For nivolumab administration, specific precautionary measures outlined in section 7.6.2 must be applied.

